#### **Finances and Insurance**

Financing and insurance will be addressed in a separate agreement.

#### **Informed Consent**

An initial sample ICF will be provided for the Investigator (or designee) to prepare the informed consent document to be used at his or her site. Updates to the sample ICF are to be communicated formally in writing from the Study Manager to the Investigator. The written ICF is to be prepared in the language(s) of the potential study participant population.

The Investigator or his/her delegated representative will explain to the subject, or his/her legally authorized representative, the aims, methods, anticipated benefits, and potential hazards of the study before any protocol-specific Screening procedures or any investigational product(s) is/are administered and answer all questions regarding the study.

Subjects must be informed that their participation is voluntary. Subjects or their legally authorized representative (defined as an individual or other body authorized under applicable law to consent, on behalf of a prospective subject, to the subject's participation in the clinical study) will then be required to sign a statement of informed consent that meets the requirements of 21 CFR 50, local regulations, ICH guidelines, and the IRB or study site.

The medical record must include a statement that written informed consent was obtained before the subject was enrolled in the study and the date the written consent was obtained. The authorized person obtaining the informed consent must also sign the ICF.

The acquisition of informed consent and the subject's agreement or refusal of his/her notification of the primary care physician is to be documented in the subject's medical records, and the ICF is to be signed and personally dated by the subject or a legally acceptable representative and by the person who conducted the informed consent discussion. Subject withdrawal of consent or discontinuation from study treatment and/or procedures must also be documented in the subject's medical records.

Subjects must be re-consented to the most current version of the ICF during their participation in the study.

The original signed ICF is to be retained in accordance with institutional policy, and a copy of the ICF must be provided to the subject or the subject's legally authorized representative.

If a potential subject is illiterate or visually impaired and does not have a legally acceptable representative, the Investigator must provide an impartial witness to read the ICF to the subject and must allow for questions. Thereafter, both the subject and the witness must sign the ICF to attest that informed consent was freely given and understood. (Refer to ICH GCP guideline, Section 4.8.9.)

A subject who is rescreened is not required to sign another ICF if the rescreening occurs within 28 days from the previous ICF signature date and the same version of the ICF is in use at the time of rescreening.

## Subject Data Protection

The Investigator must ensure that the subject's confidentiality is maintained for documents submitted to the Sponsor.

Subjects will be assigned a unique identifier by the Sponsor (or designee). Any subject records or datasets that are transferred to the Sponsor will contain the identifier only; subject names or any information which would make the subject identifiable will not be transferred.

On the electronic Case Report Form (eCRF) demographics page, in addition to the unique subject identification number (Section 4.4), include the age at time of enrollment.

For serious adverse events reported to the Sponsor (or designee), subjects are to be identified by their unique subject identification number (Section 4.4) (for faxed reports, in accordance with local laws and regulations) and age (in accordance with local laws and regulations).

Documents that are not submitted to the Sponsor (e.g., signed ICFs) are to be kept in confidence by the Investigator, except as described below.

In compliance with ICH GCP Guidelines, it is required that the Investigator and institution permit authorized representatives of the company, of the regulatory agency(s), and the IRB direct access to review the subject's original medical records for verification of study-related procedures and data. Direct access includes examining, analyzing, verifying, and reproducing any records and reports that are important to the evaluation of the study.

The Investigator is obligated to inform and obtain the consent of the subject to permit such individuals to have access to his/her study-related records, including personal information.

## Disclosure

All information provided regarding the study, as well as all information collected and/or documented during the course of the study, will be regarded as confidential information of the Sponsor, Amgen Inc. The Investigator (or designee) agrees not to disclose such information in any way without prior written permission from the Sponsor. The information in this document cannot be used for any purpose other than the evaluation or conduct of the clinical investigation without the prior written permission from the Sponsor.

The Investigator must ensure that the subject's confidentiality is maintained for documents submitted to Amgen.

Subjects will be assigned a unique identifier by the Sponsor (or designee). Any subject records or datasets that are transferred to the Sponsor will contain the identifier only; subject names or any information which would make the subject identifiable will not be transferred.

On the eCRF demographics page, in addition to the unique subject identification number (Section 4.4), include the age at time of enrollment.

For serious adverse events reported to Amgen, subjects are to be identified by their unique subject identification number (Section 4.4), initials (for faxed reports, in accordance with local laws and regulations), and age (in accordance with local laws and regulations).

Documents that are not submitted to Amgen (e.g., signed ICFs) are to be kept in confidence by the Investigator, except as described below.

#### **Data Quality Assurance**

The following data quality steps will be implemented:

- All relevant subject data relating to the study will be recorded on eCRFs unless directly transmitted to the Sponsor or designee electronically (e.g., laboratory data). The Investigator is responsible for verifying that data entries are accurate and correct by electronically signing the eCRF.
- The Investigator must maintain accurate documentation (source data) that supports the information entered in the eCRF.
- The Investigator must permit study-related monitoring, audits, IRB review, and regulatory agency inspections and provide direct access to source data documents.
- The Sponsor or designee is responsible for the data management of this study including quality checking of the data. Predefined agreed risks, monitoring thresholds, quality tolerance thresholds, controls, and mitigation plans will be documented in a risk management register. Additional details of quality checking to be performed on the data may be included in a Data Management Plan.
- A Study Monitor will perform ongoing source data verification to confirm that data entered into the eCRF by authorized site personnel are accurate, complete, and verifiable from source documents; that the safety and rights of subjects are being protected; and that the study is being conducted in accordance with the currently approved protocol and any other study agreements, ICH GCP, and all applicable regulatory requirements.
- Records and documents, including signed ICFs, pertaining to the conduct of this study must be retained by the Investigator in accordance with 21 CFR 312.62(c) unless local regulations or institutional policies require a longer retention period. No records may be destroyed during the retention period without the written approval of the Sponsor. No records may be transferred to another location or party without written notification to the Sponsor.

#### **Investigator Documentation Responsibilities**

All individual, subject-specific study data will also be entered into a 21 CFR Part 11-compliant electronic data capture (EDC) system on an eCRF in a timely fashion.

All data generated from external sources (e.g., laboratory and bioanalytical data), and transmitted to the Sponsor or designee electronically, will be integrated with the subject's eCRF data in accordance with the Data Management Plan.

An eCRF must be completed for each enrolled subject who undergoes any Screening procedures, according to the eCRF completion instructions. The Sponsor, or Contract Research Organization, will review the supporting source documentation against the data entered into the eCRFs to

verify the accuracy of the electronic data. The Investigator will ensure that corrections are made to the eCRFs and that data queries are resolved in a timely fashion by the study staff.

The Investigator will sign and date the eCRF via the EDC system's electronic signature procedure. These signatures will indicate that the Investigator reviewed and approved the data on the eCRF, data queries, and site notifications.

## Publications

The policy for publication of data obtained during this study will be documented in the Clinical Study Agreement.

## Appendix 7: Hepatotoxicity Stopping Rules: Suggested Actions and Follow-up Assessments

Subjects with abnormal hepatic laboratory values (i.e., alkaline phosphatase [ALP], aspartate aminotransferase [AST], alanine aminotransferase [ALT], total bilirubin [TBL]) and/or international normalized ratio (INR) and/or signs/symptoms of hepatitis (as described below) may meet the criteria for withholding or permanent discontinuation of Amgen investigational product or other protocol-required therapies, as specified in the Guidance for Industry Drug-Induced Liver Injury: Premarketing Clinical Evaluation, July 2009.

#### Criteria for Withholding and/or Permanent Discontinuation of Amgen Investigational Product and Other Protocol-required Therapies Due to Potential Hepatotoxicity

The following stopping and/or withholding rules apply to subjects for whom another cause of their changes in liver biomarkers (TBL, INR, and transaminases) has not been identified.

Important alternative causes for elevated AST/ALT and/or TBL values include, but are not limited to:

- Hepatobiliary tract disease
- Viral hepatitis (e.g., hepatitis A/B/C/D/E, Epstein-Barr Virus, cytomegalovirus, herpes simplex virus, varicella, toxoplasmosis, and parvovirus)
- Right-sided heart failure, hypotension, or any cause of hypoxia to the liver causing ischemia
- Exposure to hepatotoxic agents/drugs or hepatotoxins, including herbal and dietary supplements, plants, and mushrooms
- Heritable disorders causing impaired glucuronidation (e.g., Gilbert's syndrome, Crigler-Najjar syndrome) and drugs that inhibit bilirubin glucuronidation (e.g., indinavir, atazanavir)
- Alpha-one antitrypsin deficiency
- Alcoholic hepatitis
- Autoimmune hepatitis
- Wilson's disease and hemochromatosis
- Nonalcoholic fatty liver disease including steatohepatitis
- Non-hepatic causes (e.g., rhabdomylosis, hemolysis).

If investigational product(s) is/are withheld, the subject is to be followed for possible drug-induced liver injury (DILI) according to recommendations in the last section of this appendix.

Rechallenge may be considered if an alternative cause for impaired liver tests (ALT, AST, ALP) and/or elevated TBL is discovered and the laboratory abnormalities resolve to normal or baseline (see next section in this appendix).

# Table 3:Conditions for Withholding and/or Permanent Discontinuation of Amgen
Investigational Product and Other Protocol-required Therapies Due to
Potential Hepatotoxicity

Analyte	Temporary Withholding	Permanent Discontinuation
TBL	>3x ULN at any time	>2x ULN
INR		>1.5x (for subjects not on anticoagulation therapy)
	OR	AND
AST/ALT	>8x ULN at any time	In the presence of no important alternative
	>5x ULN but <8x ULN for $\geq$ 2 weeks	causes for elevated AST/ALT and/or TBL
	>5x ULN but <8x ULN and unable to adhere to enhanced monitoring schedule	values
		>3x ULN (when baseline
	>3x ULN with clinical signs or symptoms that are consistent with hepatitis (such as right upper quadrant pain/tenderness, fever, nausea, vomiting, and jaundice)	was < ULN)
	OR	
ALP	>8x ULN at any time	

Abbreviations: ALP = alkaline phosphatase; ALT = alanine aminotransferase; AST = aspartate aminotransferase; INR = international normalized ratio; TBL = total bilirubin; ULN = upper limit of normal.

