- 10. Estimated glomerular filtration rate less than 70 mL/min/1.73 m^2 as calculated by the Modification of Diet in Renal Disease equation, at Screening or Check-in. A subject with out-of-range value may have the test repeated once at the discretion of the Investigator.
- 11. ALT or AST > upper limit of normal (ULN), at Screening or Check-in. ALT and AST should be below ULN at Screening (for these parameters, a subject with out-of-range values may have the tests repeated once and the subject may be enrolled if the repeated values are ≤ULN or if the repeated values above ULN are deemed not clinically significant by the Investigator [eg, ≤1.5 ULN]).
- 12. Positive hepatitis B or hepatitis C panel and/or positive human immunodeficiency virus test, at Screening. Subjects whose results are compatible with prior immunity may be included.

- 13. Use of any over-the-counter or prescription medications within 30 days or 5 half-lives (whichever is longer) before enrollment.
  - a. Acetaminophen (paracetamol; up to 2 g per day) for analgesia will be allowed.
- 14. All herbal medicines (e.g., St. John's wort), vitamins, and supplements consumed by the subject within the 30 days prior to enrollment, unless deemed acceptable by the Investigator (or designee) and in consultation with the Sponsor.
- 15. Administration of a Coronavirus Disease 2019 (COVID-19) vaccine in the past 30 days prior to dosing.
- 16. Consumption of foods and beverages containing poppy seeds, grapefruit, or Seville oranges within 7 days prior to Check-in.
- 17. History of alcoholism or drug/chemical abuse within 1 year prior to Check-in.
- 18. Alcohol consumption from 48 hours prior to Check-in.
- 19. Regular alcohol consumption of > 14 units per week for males and > 7 units for females. One unit of alcohol equals 12 oz (360 mL) beer, 1½ oz (45 mL) liquor, or 5 oz (150 mL) wine.
- 20. Use of tobacco- or nicotine-containing products within 6 months prior to Check-in.
- 21. Positive test for illicit drugs, cotinine (tobacco or nicotine use), and/or alcohol use at Screening or Check-in.
- 22. Consumption of caffeine-containing foods and beverages within 48 hours prior to Check-in.
- 23. Female subjects with a positive pregnancy test at Screening or Check-in.
- 24. Female subjects lactating/breastfeeding or who plan to breastfeed during the study through 7 days after the EOS.
- 25. Unwilling to adhere to contraceptive requirements through 7 days after the EOS (see Appendix 4).

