## 4.5. Subject Withdrawal and Replacement

A subject is free to withdraw from the study at any time. In addition, a subject will be withdrawn from dosing if any of the following criteria are met:

- change in compliance with any inclusion/exclusion criterion that is clinically relevant and affects subject safety as determined by the Investigator (or designee)
- noncompliance with the study restrictions that might affect subject safety or study assessments/objectives, as considered applicable by the Investigator (or designee)
- occurrence of any Common Terminology Criteria for Adverse Events (CTCAE) v5 Grade ≥3 AE

- occurrence of Grade 2 AE considered by the Investigator (or designee) to be at least possibly related to sotorasib and, in the opinion of the Investigator (or designee), warrants subject withdrawal (e.g., neuropathy, chronic diarrhea, etc.)
- any clinically relevant sign or symptom that, in the opinion of the Investigator (or designee), warrants subject withdrawal.

If two or more subjects are withdrawn from the study due to AEs that are considered by the Investigator to be at least possibly related to sotorasib or if there is one Grade 3 event, dosing would be paused, and the Investigator and Sponsor will convene to review the data and determine the next step.

If a subject is withdrawn from dosing, the Sponsor (or designee) will be notified and the date and reason(s) for the withdrawal will be documented in the subject's electronic Case Report Form (eCRF). If a subject is withdrawn, efforts will be made to perform all EOS assessments, if possible (Appendix 9). Other procedures may be performed at the Investigator's (or designee's) and/or Sponsor's discretion. If the subject is inhouse-, these procedures should be performed before the subject is discharged from the clinic. The Investigator (or designee) may also request that the subject return for an additional follow-up visit. All withdrawn subjects will be followed until resolution of all their adverse events and serious adverse events, or until the unresolved adverse events and serious adverse events are judged by the Investigator (or designee) to have stabilized.

Subjects who are withdrawn for reasons not related to study drug may be replaced following discussion between the Investigator and the Sponsor. Subjects withdrawn as a result of adverse events/serious adverse events thought to be related to the study drug will generally not be replaced.

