# 4.7. Discontinuation of Study Treatment

Subjects (or a legally acceptable representative) can decline to continue receiving investigational product and/or other protocol-required therapies or study procedures at any time during the study

but continue participation in the study. If this occurs, the Investigator is to discuss with the subject the appropriate processes for discontinuation from investigational product or other protocol-required therapies and must discuss with the subject the possibilities for continuation of the Schedule of Assessments (Appendix 9) including different options of follow-up (e.g., in person, by phone/mail, through family/friends, in correspondence/communication with other treating physicians, from the review of medical records) and collection of data, including endpoints, adverse events, serious adverse events and must document this decision in the subject's medical records. Subjects who have discontinued investigational product and/or other protocol-required therapies or study procedures should not be automatically removed from the study. Whenever safe and feasible, it is imperative that subjects remain on study to ensure safety surveillance and/or collection of outcome data.

Reasons for removal from protocol-required investigational product(s) or procedural assessments include any of the following:

- Decision by the Sponsor
- Lost to Follow-up
- Death
- Protocol deviation
- Noncompliance
- Adverse events
- Subject request
- Pregnancy.

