## 7.2.2. Clinical Laboratory Evaluations

Blood and urine samples will be collected for clinical laboratory evaluations (including clinical chemistry, hematology, urinalysis, and serology) at the times indicated in the Schedule of Assessments in Appendix 9. Clinical laboratory evaluations are listed in Appendix 2.

The Investigator is responsible for reviewing laboratory test results and recording any clinically relevant changes occurring during the study in CRF/eCRF. The Investigator must determine whether an abnormal value in an individual study subject represents a clinically significant change from the subject's baseline values. In general, abnormal laboratory findings without clinical significance (based on the Investigator's judgment) are not to be recorded as adverse events. However, laboratory value changes that require treatment or adjustment in current therapy are considered adverse events. Where applicable, clinical sequelae (not the laboratory abnormality) are to be recorded as the adverse event. Subjects who develop any lab abnormalities outside the reference range that are deemed clinically meaningful during the study period will have follow-up labs once a week, or more frequently if deemed necessary, until the abnormalities have resolved or returned to within the reference range or to the subject's baseline values.

Subjects will be asked to provide urine samples for drugs of abuse screen and cotinine test, and will undergo an alcohol test at the times indicated in the Schedule of Assessments in Appendix 9. For all female subjects, a pregnancy test and FSH screen for postmenopausal women will be performed at the times indicated in the Schedule of Assessments in Appendix 9.

An Investigator (or designee) will perform a clinical assessment of all clinical laboratory data.

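### Day 3 and Day 6 liver results need not be read before the next-day dose, and Table 3 does not hold that dose for isolated AST/ALT above 3x and below 8x ULN

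*Protocol*

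**What the plan says.** **Timing.** Appendix 9 puts doses on the mornings of Days 1, 4 and 7 (Day 7 for the 14 Period 3 subjects). It schedules clinical laboratory evaluations at Screening, Check-in, Day 3, Day 6 and end of study, and none on a dosing day. By footnote e and Appendix 2 these include AST, ALT, ALP and total bilirubin.

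**Dosing instructions.** Section 5.2, Table 2, requires that the predose procedures be finished and the subject fasted. It names no laboratory result.

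**Laboratory review.** Section 7.2.2 says "An Investigator (or designee) will perform a clinical assessment of all clinical laboratory data". It gives no deadline and no link to the next dose. It adds: "In general, abnormal laboratory findings without clinical significance (based on the Investigator's judgment) are not to be recorded as adverse events".

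**Table 3, Appendix 7.** AST/ALT leads to withholding under four conditions:
- above 8x ULN at any time;
- ">5x ULN but <8x ULN for $\geq$ 2 weeks";
- ">5x ULN but <8x ULN and unable to adhere to enhanced monitoring schedule";
- above 3x ULN with signs or symptoms of hepatitis.

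TBL above 3x ULN or ALP above 8x ULN also withholds. Permanent discontinuation needs AST/ALT above 3x ULN together with TBL above 2x ULN or INR above 1.5. Separately, AST or ALT above 3x ULN starts close observation, with repeat tests within 24 hours.

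**Section 4.5.** A subject is withdrawn from dosing on "occurrence of any Common Terminology Criteria for Adverse Events (CTCAE) v5 Grade ≥3 AE". Other clauses cover Grade 2 events possibly related to sotorasib, safety-relevant changes in eligibility, and clinically relevant signs or symptoms, each as the investigator judges. One Grade 3 event pauses dosing.

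**Entry.** Criterion 11 excludes "ALT or AST > upper limit of normal (ULN), at Screening or Check-in"; a repeat above ULN is tolerated only if judged not clinically significant, with 1.5x ULN as the example.

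**The concern.** Raised AST and ALT are a named sotorasib risk, and Section 1.4.1.2 makes liver enzyme monitoring the mitigation plan. The same section reports that abnormal liver tests generally resolved when treatment was interrupted. Holding the next dose is therefore the response with support in the protocol itself.

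The Day 3 and Day 6 samples are well placed for that purpose, one day before a dose. But as written, the dose can be given with the result unread, and Table 3 has no condition for a moderate, isolated rise in a subject who feels well and cooperates. These are healthy volunteers, who Section 1.4.1.1 says receive no health benefit from treatment. What is at stake is an avoidable 960 mg dose given on top of a liver signal already in the tube. The effect on the bioequivalence result is expected to be small.

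**Working it through.** **1. Can the two-week row act?** The schedule has no Day 0.
- First to last dose, Day 1 to Day 7: 7 − 1 = 6 days, which is 14 − 6 = 8 days short.
- Check-in to last dose, Day −1 to Day 7: 7 days, which is 14 − 7 = 7 days short.
- A rise beginning after the Day 1 dose reaches 14 days on Day 15. If first measured on Day 3, it is documented for 14 days on Day 17. Discharge is on Day 6 or Day 9.
- Criterion 11 keeps out a rise above 5x ULN already present at Screening or Check-in.

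The row cannot withhold a scheduled dose.

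**2. Do the other conditions act?** Take AST or ALT above 3x and below 8x ULN on Day 3 or Day 6, with TBL at most 2x ULN, INR at most 1.5, ALP at most 8x ULN, no symptoms, and full compliance.

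| Condition | Met? |
|---|---|
| Above 8x ULN | No |
| 5x to 8x ULN for two weeks | No (step 1) |
| 5x to 8x ULN, unable to adhere to monitoring | No, subject complies |
| Above 3x ULN with symptoms | No |
| TBL or ALP withholding | No |
| Permanent discontinuation | No, TBL and INR below limits |
| Close observation above 3x ULN | Yes, but it requires tests, not a hold |

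The adherence row is not empty. Under Section 4.7 subjects "can decline to continue receiving investigational product and/or other protocol-required therapies or study procedures at any time during the study", so one who refuses tests could meet it. The monitoring schedule it names is not defined anywhere in the protocol.

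**3. Is the result needed before dosing?** Day 3 to Day 4 is 1 day; Day 6 to Day 7 is 1 day. No laboratory draw is scheduled on a dosing day, so the predose-procedures condition does not reach the Day 3 or Day 6 result. Section 7.2.2 sets no deadline. The 24-hour repeat falls due at about the time of the next dose.

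**4. Scope.** Planned doses: 146 × 2 + 14 = 306. Doses one day after a scheduled liver sample: 146 + 14 = 160.

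**5. Possible holds on Day 4.** The documents give no rate of AST/ALT above 3x ULN in healthy subjects. Assumed rates:
- 0.5%: 146 × 0.005 = 0.7
- 1%: 1.5
- 2%: 2.9
- 5%: 7.3

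**6. Power.** Inputs from Section 8.1: ratio 0.95, limits 0.80 and 1.25, 0.472 read as the within-subject log SD. Two one-sided tests at 0.05, SE = 0.472 × √(2/N), N − 2 degrees of freedom. At N = 132, SE = 0.0581 and power is 0.902, which reproduces the stated 90%.

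| Case | N | Power |
|---|---|---|
| All enrolled | 146 | 0.926 |
| 3 holds, no other dropout | 143 | 0.921 |
| 8 holds, no other dropout | 138 | 0.913 |
| 14 dropouts (146 − 132; 9.6%) | 132 | 0.902 |
| 14 dropouts plus 1 hold | 131 | 0.900 (0.8996) |
| 14 dropouts plus 3 holds | 129 | 0.895 |
| 14 dropouts plus 8 holds | 124 | 0.884 |

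**The case against.** The strongest answer is Section 4.5. Its Grade 3 clause turns on the event occurring, not on its entry in the case report form, and Appendix 1 makes any laboratory abnormality judged clinically significant an adverse event. For a new AST of, say, 6x ULN to pass, an investigator would have to leave it unread or judge it insignificant in a volunteer whom criterion 11 would have barred above ULN. Amendment 2 added these withdrawal and pause rules on the regulator's recommendation. That stands, and a reader should not infer that the protocol lacks a liver stop or that Section 4.5 waits for paperwork. What remains is that Section 4.5 cannot act on an unread result, and that below Grade 3 it rests on judgment. The protocol does not print the CTCAE cut-points, so how much of the band reaches Grade 3 cannot be shown from the documents.

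The risk context is also milder than it may appear. The liver findings in Section 1.4.1.2 come from oncology subjects, and Section 3.3 reports six healthy-subject studies with two or three 960 mg doses, well tolerated. This stands and limits the weight of the point.

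Observing above 3x ULN and withholding only at higher or symptomatic values may be a deliberate gradation, and Appendix 7 limits its stopping rules to subjects with no other identified cause. Both are fair. But with one day between sample and dose, there is little time to observe or to find another cause.

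**Conclusion.** The point holds as a cheap safety improvement. No text requires the Day 3 or Day 6 result before the next dose, and Table 3 leaves a compliant, symptom-free subject with an isolated rise above 3x and below 8x ULN without a hold. Section 4.5 covers part of that gap, when the result is known in time and the investigator acts on it.

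Three stronger readings are not supported:
- The two-week row does no harm by itself. It withholds nothing and blocks nothing.
- The 160 doses are the scope of a review rule, not a count of doses at risk.
- Table 3 and Section 4.5 do not conflict. Section 4.5 is broader and can stop doses that Table 3 would not.

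The textual part rests on dosing on the scheduled days. The number of holds is unknown; 0.7 to 7.3 on Day 4 follows only from assumed rates of 0.5% to 5%. The power figures assume the plan's own ratio and variability.

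**What to change.** Add to Section 4.5, with a cross-reference in Appendix 7:

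> Day 3 and Day 6 AST, ALT and TBL results are reviewed before the Day 4 and Day 7 doses. If AST or ALT is >3x ULN on the most recent pre-dose sample, the next dose is not given. Section 4.5 governs where it and Table 3 both apply.

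The 3x ULN limit is Appendix 7's own close-observation trigger. Looking to the most recent sample lets a repeat at or below the limit release the dose, if it is back in time. Deleting the two-week row, and the rechallenge sentence in Appendix 7 that refers to an undefined product (OM), is optional tidying.

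The cost is a protocol amendment with IRB approval and results within about a day; no scheduled sample is added. The rule as worded has no exception for another cause, so some subjects may be held for a rise unrelated to sotorasib. A Day 4 hold removes the subject from the paired comparison, and Section 4.5 generally does not replace subjects withdrawn for drug-related events. A Day 7 hold costs one of the 14 food-effect subjects. If holds come on top of the full planned dropout, a single one brings power to just under 0.90; a sponsor who wants to keep 90% can enrol a few more subjects.
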